### 7.1 Treatment Schedule

#### 7.11 Consolidation 1 (Cycles 1-2 or 1-4, as the case may be for that patient)

Agent	Dose	Route	Day	Cycles
Daratumumab	16 mg/Kg* (IV) 1,800 mg (Injection)	IV or injection	1, 8, 15, 22	Cycle 1-2
Daratumumab	16 mg/Kg* (IV) 1,800 mg (injection)	IV or injection	1, 15	Cycle 3-4

Cycle 1 (to 3, as the case may be for that patient) length = 28 days;  
 Cycle 2 (or 4, as the case may be for that patient) length = up to 84 days (4 weeks treatment + window period up to 8 weeks between Consolidation 1 and ASCT)  
 Treatment Window (for patients receiving treatment through a local medical doctor)=  $\pm 5$  days

\*Any dose-adjustments will be made as per the prescriber information.

Daratumumab administration as per prescriber information and institutional guidelines.

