## 10.6 Required Routine Reporting

### 10.61 Baseline and Adverse Events Evaluations

Pretreatment symptoms/conditions to be graded at baseline and adverse events to be graded at each evaluation.

Grading is per CTCAE v4.0 **unless** alternate grading is indicated in the table below:

System Organ Class (SOC)	Adverse event/Symptoms	Baseline	Each evaluation
Blood and lymphatic system disorders	Anemia		X
Skin and subcutaneous tissue disorder	Rash Maculo-papular		X*
General disorders and administration site conditions	Infusion related reaction		X
	Injection site reaction		X
	Fatigue	X	X
Investigations	Neutrophil count decreased		X
	Platelet count decreased		X

\*Only for evaluations during cycles 4-15

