#### 15.18 Nursing Guidelines

- Daratumumab can cause severe infusion reactions, usually during the first infusion. Patients who have experienced a reaction may experience further reactions with subsequent infusions. Most reactions occur during or within 4 hours of infusion, however, may occur up to 48 hours after an infusion. Warn patient of this possibility. Monitor patient throughout infusion for bronchospasm, hypoxia, SOB, and hypertension. Patients may also experience symptoms of anaphylaxis. Administer emergency medication as ordered.
- Patients may experience infections, including URI and pneumonia. Patients who have an ongoing infection should not receive agent.
- Patients may experience gastrointestinal side effects including diarrhea and nausea. Treat symptomatically and monitor for effectiveness.
- Warn patients about the possibility of peripheral neuropathy, dizziness, and insomnia.
- Fatigue is common. Instruct patient in energy conserving lifestyle.
- Rarely patients may experience cardiac issues including, atrial-fibrillation, peripheral edema, and hypertension. Instruct patient to report any chest pain, heart palpitations, and swelling to the study team.
- Monitor CBC w/diff as cytopenias (thrombocytopenia, neutropenia, anemia, and lymphopenia) have been seen. Instruct patient to report any unusual, bruising, bleeding, and/or infections/fever to the study team.

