#### 16.42 Secondary Outcome Analyses

The rate of MRD negative response after pre-SCT consolidation with Daratumumab will be estimated by the number of patients who achieve MRD negative status by flow cytometry (MPF) in the bone marrow after pre-SCT consolidation with Daratumumab divided by the total number of evaluable patients. Exact binomial 95% confidence intervals for the true rate of MRD negative response after pre-SCT consolidation with Daratumumab will be calculated.

The rate of MRD negative response after 1 year (12 cycles) of Daratumumab and lenalidomide maintenance will be estimated by the number of patients who achieve MRD negative status by flow cytometry (MPF) in the bone marrow after 1 year of maintenance therapy divided by the total number of evaluable patients. Exact binomial 95% confidence intervals for the true rate of MRD negative response after 1 year of maintenance will be calculated.

Progression-free survival time is defined as the time from registration to the time of progression or death due to any cause. Patients who are alive and progression-free will be censored on the date of their last disease assessment. Patients who receive subsequent treatment for myeloma before disease progression will be censored on the date of their last disease assessment prior to initiation of the subsequent treatment. The distribution of progression-free survival will be estimated using the method of Kaplan-Meier.

Survival time is defined as the time from registration to death due to any cause. The distribution of survival time will be estimated using the method of Kaplan-Meier.

The overall response rate at day 100 post ASCT will be estimated by the number of patients with an objective status of sCR, CR, VGPR, or PR at the day 100 post ASCT assessment divided by the total number of evaluable patients. Response assessment will be in comparison to values obtained at the disease assessment at the time registration. Exact binomial 95% confidence intervals for the true overall response rate at day 100 post ASCT will be calculated.

**Adverse Events:** All eligible patients that have initiated treatment will be considered evaluable for assessing adverse event rate(s). The maximum grade for each type of adverse event will be recorded for each patient, and frequency tables will be reviewed to determine patterns. Additionally, the relationship of the adverse event(s) to the study treatment will be taken into consideration.

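### The single adverse event denominator in 16.42 dilutes the injection site reaction rate, and possibly the infusion related reaction rate, with patients never given that route

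*Combined protocol and SAP*

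**What the plan says.** The treatment tables in 7.11 (consolidation 1) and 7.13 (maintenance) both offer two routes for daratumumab: "16 mg/Kg* (IV) 1,800 mg (Injection". Consolidation 2 (7.12) contains no daratumumab. No rule assigns the route and no expected split is given; 7.11 says only "Daratumumab administration as per prescriber information and institutional guidelines". Route is not a grouping factor (5.0) or a descriptive factor (12.0).

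Section 10.61 lists seven terms to be graded at each evaluation. Two are linked to the route: "Infusion related reaction" and "Injection site reaction". Neither is limited to patients who had that route. Another term in the same table, maculo-papular rash, does carry a limit: "Only for evaluations during cycles 4-15".

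For the analysis, 16.42 states "All eligible patients that have initiated treatment will be considered evaluable for assessing adverse event rate(s" and then "The maximum grade for each type of adverse event will be recorded for each patient, and frequency tables will be reviewed to determine patterns". No section defines a denominator of patients exposed to a given route, or a table by route.

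**The concern.** A rate is easiest to interpret when everyone in the denominator could have had the event. A patient who was only ever infused cannot have an injection site reaction, yet counts in the denominator for it. The planned figure therefore depends on two things: how often the reaction follows an injection, and how many patients happened to be injected. The second is not controlled by the protocol and would not carry over to another setting.

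Infusion related reaction raises the same question less firmly. Section 15.18 says "Daratumumab can cause severe infusion reactions, usually during the first infusion", which links the reaction to infusion, but it does not say that injected patients are free of it.

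At stake is how two rows of the safety table are read under objective 2.24. Someone who wants to know how often patients given one route react to it would read a figure that is too low, by an amount that the table would not reveal.

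**Working it through.** **The plan's own figures.** The protocol states no expected rate of either reaction for this trial, so there is no directly relevant figure to reproduce. The stated design figures do reproduce: continuing with at least 10 of 20 successes and requiring at least 25 of 45, the exact two-stage binomial gives 0.0903 at a true proportion of 0.45 and 0.9001 at 0.65, against the stated 0.09 and 0.90. They do not depend on the adverse event denominator.

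**Inputs**

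- Planned accrual: 50 (16.12, 45 evaluable plus 5). This is used as an upper limit for the number of eligible patients who start treatment.
- Reference bands for daratumumab (15.15): infusion related reaction is listed as very common (10% or more), injection site reaction as common (1 to <10%). They are not forecasts for this trial. Reading them as rates among patients given the route is an assumption.
- Route shares: not given. Assumed range 10% to 100%, with an even split as the worked example.

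**Formulas**

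Let *s* be the share of patients with at least one injection and *r* the injection site reaction rate among them. The rate in everyone else is zero, so

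reported rate = *s* × *r* + (1 − *s*) × 0 = *s* × *r*.

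Let *v* be the share with at least one intravenous dose, *a* the infusion related reaction rate among them and *b* the rate among patients who were only injected. Then

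reported rate = *v* × *a* + (1 − *v*) × *b*.

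**Results.** The last column sets *b* = 0, meaning reactions only after intravenous doses.

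| Share given the route | Injection site reaction, true 1 to <10% | Infusion related reaction, true 10% or more, *b* = 0 |
|---|---|---|
| 10% | 0.1 to <1% | 1% or more |
| 25% | 0.25 to <2.5% | 2.5% or more |
| 50% | 0.5 to <5% | 5% or more |
| 75% | 0.75 to <7.5% | 7.5% or more |
| 90% | 0.9 to <9% | 9% or more |
| 100% | 1 to <10% | 10% or more |

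In patients, an even split of 50 gives 25 injected. The expected number with an injection site reaction is 25 × 0.01 = 0.25 up to less than 25 × 0.10 = 2.5. Divided by 50 this is 0.5 to <5%, so the shift is below 5 percentage points.

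**How far *b* = 0 matters.** With *v* = 0.5 and *a* = 10%:

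- *b* = 0: 0.5 × 10% = 5%
- *b* = 5% (assumed): 0.5 × 10% + 0.5 × 5% = 7.5%
- *b* = 10% (assumed): 0.5 × 10% + 0.5 × 10% = 10%, no dilution

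**Patients who change route.** Nothing bars a switch. A patient who had both routes belongs in both exposed groups, so *s* + *v* can exceed 1 and the dilution shrinks. It vanishes for a route that every patient received.

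**Effect on precision.** Take 5 reactions among 25 exposed patients (assumed counts). The exposed rate is 5/25 = 20%, exact 95% interval 7% to 41%. The pooled figure is 5/50 = 10%, interval 3% to 22%. The narrower interval belongs to a different quantity.

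**The case against.** Objective 2.24 asks for the safety profile of the regimen, not of a route. A per-patient rate over all eligible patients who started treatment answers that question for the regimen as delivered. This stands, and it is why the pooled table should stay.

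Nothing in the documents makes infusion related reaction exclusive to the intravenous route, and 10.61 grades it in everyone. This also stands. Full dilution by the route share is firm only for injection site reaction, which is the term with the lower reference band. A reader might infer that both terms are understated by the same certain factor; the documents do not support that.

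It can also be said that 16.42 already has the frequency tables reviewed for patterns, so a split by route is allowed. That is true, but allowing it does not define the denominator or say how an event is assigned when a patient has had both routes.

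A reader might go further and argue that all adverse events should be tabulated by route, because 15.14 reports a mean maximum trough with injection that is 81% higher at 50 kg or less and 12% lower above 85 kg. The same section gives an overall trough ratio of 108% (90% CI 96 to 122) and describes area under the curve and peak concentration as comparable. Trough levels in any case do not determine who is at risk of an administration reaction. A main table by route of first dose would also misclassify anyone who switched.

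**Conclusion.** The concern holds for the two route-linked terms. As written, 16.42 understates the injection site reaction rate among injected patients by a factor equal to the share injected. It understates infusion related reaction among infused patients to the extent that the reaction is less frequent in patients who were only injected.

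With an assumed even split and the bands in 15.15, that is 0.5 to <5% in place of 1 to <10%, and 5% or more in place of 10% or more if only intravenous doses cause the reaction. The true size cannot be worked out from the documents, because the route mix is missing and no rule says whether an infusion-type reaction after an injection is coded under the same term.

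The effect is limited to descriptive safety reporting. The primary endpoint and the interim and final decision rules are untouched. The stopping rule in 16.52 counts grade 4 or higher non-hematologic events overall, at least possibly related to treatment, and does not use a route-specific rate. A reader might infer that objective 2.24 would go unanswered or that safety monitoring is compromised; neither follows from the text.

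**What to change.** Keep the pooled table in 16.42 as the summary for the regimen, and add three descriptive rates, each shown with its denominator:

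- injection site reaction among patients with at least one injection;
- infusion related reaction among patients with at least one intravenous dose;
- infusion-type systemic reactions after an injection, reported separately among injected patients.

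State that each event is attributed to the route of the preceding dose, and that a patient who had both routes counts in both denominators.

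The cost is a few sentences in 16.42 and one short tabulation. Treatment does not change. The documents do not show the case report form fields, so the team should confirm that route is recorded for each dose. The statistical downside is smaller denominators and wider intervals for these rates.

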### 2.2 Secondary Objectives:

- 2.21 To determine percentage of patients achieving MRD negativity by MPF after 1 year of daratumumab+lenalidomide-based maintenance therapy.
- 2.22 To determine progression-free survival (PFS) for peri-SCT treatment with daratumumab.
- 2.23 To determine percentage of MRD negativity by MPF after pre-SCT consolidation with daratumumab.
- 2.24 To determine safety profile of peri-SCT daratumumab with lenalidomide.
- 2.25 To determine the overall response rate (ORR) of patients receiving peri-SCT daratumumab for MM.
- 2.26 To determine the overall survival (OS) for patients receiving peri-SCT daratumumab for MM.

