### 10.62 Submit via appropriate MCCC Case Report Forms (i.e., paper or electronic, as applicable) the following AEs experienced by a patient and not specified in Section 10.6:

10.621 Grade 2 AEs deemed *possibly, probably, or definitely* related to the study treatment or procedure.

10.622 Grade 3 and 4 AEs regardless of attribution to the study treatment or procedure.

10.623 Grade 5 AEs (Deaths)

10.6231 Any death within 30 days of the patient's last study treatment or procedure regardless of attribution to the study treatment or procedure.

10.6232 Any death more than 30 days after the patient's last study treatment or procedure that is felt to be at least possibly treatment related must also be submitted as a Grade 5 AE, with a CTCAE type and attribution assigned.

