## 11.6 Criteria for engraftment (for hematopoietic stem cell transplant studies only)

Engraftment is defined as:

- The first day of three consecutive days on which the absolute neutrophil count (ANC)  $>500/\text{mm}^3$  and
- The first of three consecutive days with an untransfused platelet count  $>20,000/\text{mm}^3$ .

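### Section 16.42 does not split adverse events by treatment phase, so its table does not isolate toxicity on daratumumab plus lenalidomide

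*Combined protocol and SAP*

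**What the plan says.** Secondary objective 2.24 is: "To determine safety profile of peri-SCT daratumumab with lenalidomide".

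The matching analysis is the Adverse Events paragraph of Section 16.42, which has three sentences. The population is: "All eligible patients that have initiated treatment will be considered evaluable for assessing adverse event rate(s". The summary is: "The maximum grade for each type of adverse event will be recorded for each patient, and frequency tables will be reviewed to determine patterns". The last sentence adds: "Additionally, the relationship of the adverse event(s) to the study treatment will be taken into consideration". None of them names a phase, a time window or a second denominator.

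Section 7.1 takes patients through four phases in sequence:
- daratumumab alone (7.11, cycles 1-2 or 1-4);
- stem cell transplant up to the Day 100 visit (7.12);
- daratumumab plus lenalidomide (7.13, cycles 4-15 or 6-17);
- single-agent daratumumab every 3 months (7.13, from cycle 16 or 18).

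On collection, Section 10.61 says: "Pretreatment symptoms/conditions to be graded at baseline and adverse events to be graded at each evaluation". It lists anemia, neutrophil count and platelet count for every evaluation, and maculo-papular rash only for evaluations in cycles 4-15. The test schedule in Section 4.1 places adverse event monitoring within 14 days before transplant, at the Day 100 visit and at the end of each maintenance cycle.

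**The concern.** One maximum per event type keeps only the worst grade a patient ever had of that type. If the worst neutrophil or platelet grade falls in the transplant period, a lower or equal grade on daratumumab plus lenalidomide leaves no trace in the table. These are the event types where that information is most wanted: Section 15.27 lists hematologic toxicity among lenalidomide's boxed warnings, and Section 8.2 ties lenalidomide dose changes to grade 4 counts. The adverse event stopping rule in Section 16.52 counts only non-hematologic events. The 16.42 table is therefore the only pre-specified statistical summary of hematologic toxicity on the combination.

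The single denominator raises a second problem. A patient who leaves the study before maintenance cannot have an event on lenalidomide, yet is counted in the rate.

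The same section does treat MRD by phase, with one rate after pre-transplant consolidation and another after a year of maintenance. Only safety is left unsplit.

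**Working it through.** The plan gives no figure for the adverse event analysis, so there is none to reproduce. The design's operating characteristics do reproduce (alpha 0.0903 against the stated .09, power 0.9001 against 0.90), and this point does not touch them.

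**1. Can transplant-period grades enter the table?** Transplant sits inside Section 7.0, Protocol Treatment. Counts are graded at each evaluation (10.61), and one of those evaluations is the Day 100 visit (4.1). Nothing in 16.42 excludes the transplant period. However, no adverse event evaluation is scheduled at the nadir, and the documents do not say whether nadir grades are entered retrospectively at Day 100. Entry is therefore permitted and natural, but not certain.

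**2. Does the attribution sentence separate them?** Section 10.3 grades attribution to agent or procedure on five levels. Section 16.42 states no rule for using it. Because transplant is protocol treatment, an event related to study treatment may still be a transplant event. The sentence does not produce a drug-only table.

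**3. How much would pooling mask?** All rates here are assumptions. For one event type, let t be the probability of grade 3 or higher in the transplant period and d the probability in the drug phases combined, taken as independent. The pooled table then shows

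P(pooled) = 1 − (1 − t)(1 − d).

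| t | d = 0% | d = 20% | d = 40% | d = 60% |
|---|---|---|---|---|
| 0% | 0% | 20% | 40% | 60% |
| 50% | 50% | 60% | 70% | 80% |
| 80% | 80% | 84% | 88% | 92% |
| 95% | 95% | 96% | 97% | 98% |

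For example, t = 95% and d = 60% gives 1 − 0.05 × 0.40 = 98%. As d runs from 0% to 60%, the pooled figure moves by 60 × (1 − t) points: 60, 30, 12 and 3 points down the rows.

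The drug phases are themselves pooled. With assumed rates of 10% in Consolidation 1 and 20% in maintenance, d = 1 − 0.90 × 0.80 = 28%. Even with no transplant events the table would show 28%, not the 20% seen in maintenance.

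**4. How much does the denominator dilute?** Assume 45 treated patients, the evaluable maximum in Section 16.12, with M of them starting maintenance. A maintenance-only event then shows at M/45 of its rate among those exposed. With a true rate of 20%:
- M = 35: 7/35 = 20% shows as 7/45 = 15.6%;
- M = 40: 8/40 = 20% shows as 8/45 = 17.8%;
- M = 45: 9/45 = 20%, with no dilution.

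**The case against.** Several counter-arguments have force.

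- *The maximum is taken per event type, not per patient.* This stands. Transplant can mask only the same event type, and only where its grade is at least as high. Most non-hematologic types may be little affected.
- *The text does not say whole course.* True. It states no window, so pooling is the natural reading rather than a stated rule.
- *Reporting rules do not prove that transplant cytopenias are captured.* Section 10.622 requires "Grade 3 and 4 AEs regardless of attribution to the study treatment or procedure", but Section 10.62 covers only events not already specified in 10.6, and the counts are listed in 10.61. The engraftment criteria in Section 11.6, such as "The first of three consecutive days with an untransfused platelet count" above a threshold, define recovery and say nothing about how adverse events are graded or recorded. The case rests on 10.61 and the Day 100 evaluation.
- *Objective 2.24 says peri-SCT.* A whole-programme table is a partial answer to it. But the objective also names lenalidomide, which is given only in maintenance, so a maintenance table is needed on either reading.
- *Safety decisions are not affected.* The stopping rule excludes hematologic events, and the DSMB reviews safety data at least twice a year. This stands: the gap is in the planned report, not in monitoring.
- *All treated patients is a conventional denominator.* It is, and it should stay for the overall table. It does not give a rate among patients exposed to lenalidomide.

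A reader might infer that objective 2.24 cannot be answered. The documents do not support that. Adverse events are graded at each evaluation, footnote h of Section 4.1 refers to an adverse event form for the last cycle, and attribution is recorded. The data for a phase split are collected; only the analysis is not specified.

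**Conclusion.** The point holds as a gap in the specified analysis. Followed as written, Section 16.42 yields a table that does not isolate toxicity on daratumumab plus lenalidomide for event types also caused by transplant. It also understates events confined to maintenance whenever some treated patients never start that phase.

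The size cannot be stated from the documents, which give no adverse event rates and no expected number reaching maintenance. Under the assumed rates, transplant masking runs from none (t = 0%) to near-complete (t = 95%). It depends on transplant-period grades actually being recorded at Day 100. A reader might conclude that the table would show grade 4 counts in 80-100% of patients. That figure only restates an assumed transplanted fraction (36 to 45 of 45), with every transplanted patient taken as grade 4, and is not evidence of the effect's size.

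The primary endpoint, sample size, alpha and power are unaffected. The change is still worth making in advance, because a phase split chosen after the results are seen is less credible than one fixed in the plan.

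**What to change.** In Section 16.42, tabulate the maximum grade per event type per patient separately for:

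1. Consolidation 1;
2. transplant up to the Day 100 visit;
3. daratumumab plus lenalidomide maintenance (cycles 4-15, or 6-17);
4. single-agent daratumumab.

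Use as denominator the patients who started each phase, and show attribution to drug and to procedure. Assign events by phase rather than by cycle number, since cycle 4 is maintenance for some patients and consolidation for those given the optional cycles. Name table 3 as the one describing daratumumab with lenalidomide under objective 2.24, and keep the overall table as the whole-programme, peri-SCT summary.

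The cost is a short change to the analysis text and a few extra descriptive tables, with smaller and therefore less precise denominators in the later phases. No new data are needed.
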